### Feasibility

Feasibility for the purposes of this study means the ability for a patient to take the full course of their assigned treatment (minimum of six cycles) through 24 weeks, except for progression or death.

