### 10.4 Interim Analyses

The study design calls for interim futility analysis by arm. These analyses will occur separately by arm once 10 patients are on an arm and have either received at least 6 cycles of therapy or experienced a PFS event. Subsequent analyses will occur after 15 patients have either received at least 6 cycles of therapy or experienced a PFS event. The final analysis will occur after 20 patients have entered and received full therapy (6 cycles). The futility analysis is based on Bayesian hypothesis testing.

For Arm D, we take the expected ORR to be 20% if epigenetic therapy does not increase the clinical effectiveness of nivolumab alone. This estimate is based on results of the Checkmate studies (CheckMate 057 (non-squamous NSCLC) ORR = 19%; CheckMate017 (squamous cell NSCLC) ORR = 20%). We would consider the addition of epigenetic therapy encouraging if the ORR is 35% or higher. The study will stop for futility if we see 0 responses among the first 10 patients or no more than 1 response in the first 15 patients. We will not consider this Arm promising if we see 3 or fewer responders out of 20 patients. The following table provides the operating characteristics for Arm D based on 5000 simulations.

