#### 10.5 Feasibility monitoring

We will use separate Bayesian calculations to monitor the feasibility of each treatment. We define feasibility as the ability for a patient to take their full course of their assigned treatment (minimum of six cycles) through 24 weeks, except for progression or death. If there is considerable probability ( $\geq 67\%$ ) that the regimen is feasible for less than half of the patients, we will consider stopping the study. We will base the decision on the posterior probability that the treatment is not feasible ( $> 50\%$  of patients who do not progress or die before 24 weeks do not make it to 24 weeks). The prior distribution for this calculation is Uniform (0,1). We will apply the monitoring rule separately by treatment group, and the analysis will occur at the time of each interim analysis. For each treatment Arm, though, we will apply the rules to all patients pooled together, rather than separately within each subtype, since we do not expect one group to be at greater risk of toxicity than the other. We will consider stopping the study if the data indicate that the treatment regimen is feasible for less than half of all patients, where we quantify certainty as two thirds or greater (i.e., 2:1 odds it is not feasible).

Rule: Stop if there is two-thirds (2:1 odds) or greater probability that 50% or more patients cannot complete at least 6 cycles of therapy (24 weeks), unless the patient's disease progressed or the patient died. The following table shows the stopping boundaries for monitoring that starts at the fifth patient.

| Stop if not feasible for | Probability that feasibility > 50% = |
|--------------------------|--------------------------------------|
| 4 out of 5 patients.     | 0.891                                |
| 4 out of 6 patients.     | 0.773                                |
| 5 out of 7 patients.     | 0.855                                |
| 5 out of 8 patients.     | 0.746                                |
| 6 out of 9 patients.     | 0.828                                |
| 6 out of 10 patients.    | 0.726                                |
| 7 out of 11 patients.    | 0.806                                |
| 7 out of 12 patients.    | 0.709                                |
| 8 out of 13 patients.    | 0.788                                |
| 8 out of 14 patients.    | 0.696                                |
| 9 out of 15 patients.    | 0.773                                |

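### Feasibility looks are timed by a futility trigger that toxicity drop-outs do not advance, and this timing contradicts the monitoring from the fifth patient that the boundaries and operating characteristics describe

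*Combined protocol and SAP*

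**What the plan says.** Section 10.1.2 defines feasibility as taking the full assigned course ("minimum of six cycles) through 24 weeks, except for progression or death"). Section 10.5 repeats this. It stops an arm when the posterior probability, under a uniform prior, that the infeasible proportion exceeds one half is at least two thirds. The formal Rule concerns patients who "cannot complete at least 6 cycles of therapy (24 weeks), unless the" patient progressed or died. A parenthesis earlier in 10.5 limits that exception to progression or death before 24 weeks.

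On timing, 10.5 says: "We will apply the monitoring rule separately by treatment group, and the analysis will occur at the time of each interim analysis". Section 10.4 sets the first look "once 10 patients are on an arm and have either received at least 6 cycles of therapy or experienced a PFS event". It continues: "Subsequent analyses will occur after 15 patients have either received at least 6 cycles of therapy or experienced a PFS event". On the last analysis it says: "The final analysis will occur after 20 patients have entered and received full therapy (6 cycles").

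Section 10.5 then introduces its boundaries differently: "The following table shows the stopping boundaries for monitoring that starts at the fifth patient". It prints one for every n from 5 to 20, followed by a table of stopping probabilities and average sample sizes.

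On who is analysed, 10.5 says that within an arm "we will apply the rules to all patients pooled together", as opposed to separately by subtype. It does not state which patients are assessable at a look.

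**The concern.** Set side by side, 10.4 and 10.5 give two routes by which a patient advances a look: receiving 6 cycles, which 10.5 calls feasible, and having a PFS event, which 10.5 excepts if it comes before week 24. The third outcome, stopping assigned treatment without progression or death, is the only one that counts against the regimen, and it is not a route. Such patients are foreseen: Section 4.4 lets patients with adverse events drop azacitidine and entinostat after two cycles and continue nivolumab alone. They may stay progression-free for months.

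This is the only numerical tolerability boundary in Section 10; Section 10.6 only tabulates toxicities. A tolerability check that is delayed by intolerance works against its purpose, and most of the arm may be enrolled before it is first applied. Readers of the operating-characteristics table would also credit the rule with a sensitivity and an early stop that the stated timing does not deliver.

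**Working it through.** **1. Boundaries.** For x infeasible among n, stop if P(Beta(1+x, 1+n−x) > 0.5) ≥ 2/3. All 16 printed boundaries and posterior values reproduce, for example 4 of 5 (0.891), 6 of 10 (0.726) and 9 of 15 (0.773).

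**2. The plan's operating characteristics.** An exact binomial recursion with N = 20, a look after every patient from the fifth and the printed boundaries does not quite reproduce the table. It matches to within 1 percentage point if the first boundary is 3 of 5. That boundary has posterior 0.656, below 2/3, and is not the one printed.

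**3. Looks at 10 and 15 only, printed boundaries.** Stop probability = P(X10 ≥ 6) + P(X10 ≤ 5 and X15 ≥ 9), with exactly 10 and then 15 assessable patients.
- Risk 0.50: 0.377 + 0.053 = 0.430
- Risk 0.60: 0.633 + 0.076 = 0.709
- Risk 0.70: 0.850 + 0.061 = 0.910 (rounded after adding)

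Expected N at 0.60 = 10 × 0.633 + 15 × 0.076 + 20 × 0.291 = 13.3. The plan prints 8.3.

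| True risk not feasible | Printed table | Printed boundaries, n = 5 to 20 | Looks at 10 and 15 | Looks at 10, 15 and 20 |
|---|---|---|---|---|
| 0.50 | 67.5% | 61.6% | 43.0% | 52.1% |
| 0.60 | 88.3% | 86.4% | 70.9% | 81.6% |
| 0.70 | 98.2% | 97.7% | 91.0% | 96.6% |

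Most of the shortfall comes from the look schedule. At 0.60 it is 86.4 − 70.9 = 15.5 points, against 88.3 − 86.4 = 1.9 points from the table mismatch.

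**4. Timing of the first look (simulation).** From the plan: 20 patients per arm, 5 patients per month overall, and the 10.4 trigger. Assumed: equal split across arms (5/3 per month each), exponential PFS, and a constant toxicity-stop hazard of −ln(1−t)/5.52 per month. Here t is the 24-week risk and 24 weeks = 168/30.4375 = 5.52 months. Toxicity drop-outs enter the trigger only at their PFS event.

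| Median PFS | Toxicity-stop risk | First look (months) | Enrolled of 20 |
|---|---|---|---|
| 4 months | almost none (1%) | 9.5 | 15.9 |
| 4 months | 50% | 10.2 | 16.7 |
| 4 months | 75% | 10.4 | 17.1 |
| 8 months | almost none (1%) | 10.5 | 17.1 |
| 8 months | 50% | 11.9 | 18.6 |
| 8 months | 75% | 13.1 | 19.2 |

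At 50 to 75% risk the look therefore slips by about 0.5 to 2.5 months relative to almost no toxicity drop-out. With medians of 3 to 12 months, the first look falls at about 9 to 13.5 months with about 16 to 19.5 enrolled.

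**5. Dependence on the analysis set.** Same accrual assumption, 60% toxicity-stop risk, median PFS 3 to 12 months, looks triggered at 10 and 15, at least 5 assessable patients:
- all enrolled patients with a known outcome, early progressions excluded: stops 88 to 93%
- the same, with early progressions kept as not failing: 13 to 61%
- trigger set only, drop-outs counted once any PFS event occurs: 38 to 61%
- trigger set only, drop-outs counted only if that event falls after 24 weeks: 2 to 18%
- trigger set only, every PFS event excepted: 0%

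**The case against.** The strongest reply is that a look trigger is not an analysis set. Section 10.4 says when an analysis happens. Nothing in 10.5 limits the feasibility data to the patients who triggered it, and its definition of failure covers toxicity drop-outs. That stands. A reader might infer that drop-outs are screened out and that the rule can hardly ever stop. The documents do not support this. A stop probability of 0% needs both the trigger set as the analysis set and an exception for PFS events at any time, whereas the 10.5 parenthesis times the exception before 24 weeks. If all enrolled patients with a known outcome count, the rule stops about 88 to 93% of the time at 60% risk.

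That figure is not clean reassurance. It depends on an unstated denominator. It is also raised because drop-outs become known before completers, and because excluding early progressions lifts the infeasible share among the rest: on the same reading the rule stops 14 to 27% of the time at 30% risk, against 11.3% under monitoring from the fifth patient with the printed boundaries.

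Three further points have some force.
- The fifth-patient wording and the boundary for every n suggest that continuous monitoring may be what was meant. If so, the timing sentence is what needs correcting.
- Section 10.4 does not say that the 6 cycles must be of the combination, so a patient continuing nivolumab alone might advance the look. The text leaves this open.
- The rule is partly advisory, and Section 6 provides safety-committee oversight and SAE reporting. This lowers the stakes without repairing the rule. The 58.3% (14/24) in Arm A who could not receive two months of priming (Section 2.4.1) concerned a different schedule and was partly due to progression, so it is only indirect evidence of risk here.

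**Conclusion.** The concern holds for the trigger and the schedule. That toxicity drop-outs do not advance the look until a PFS event follows from comparing 10.4 with 10.5 (taking the 6 cycles as the assigned combination) and needs no simulation. The contradiction between interim-only looks and monitoring from the fifth patient is explicit. Its effect with 10 and 15 assessable patients is exact: 43%, 71% and 91% against the printed 67.5%, 88.3% and 98.2%, with expected N of 13.3 against 8.3 at risk 0.60. A small part of that gap is the printed table's own mismatch with its boundaries.

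The timing figures (first look at about 10 to 13 months, about 17 to 19 of 20 enrolled, about 0.5 to 2.5 months later at 50 to 75% infeasibility) rest on equal accrual across arms, exponential PFS with medians of 4 to 8 months, and a constant toxicity-stop hazard. The documents give none of these. The plan should be changed, but it should not be described as removing drop-outs from the analysis or as unable to stop an intolerable regimen.

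**What to change.** In 10.5, separate the feasibility looks from the futility trigger.
- Apply the printed boundaries from the fifth patient, as the table assumes, to consecutive patients by enrolment order whose feasibility outcome is known: completed 6 cycles, permanently stopped assigned treatment, progressed or died, or reached 24 weeks from first dose.
- Count a stop before 24 weeks for a reason other than progression or death as infeasible, even if a PFS event follows.
- State that patients who progress or die first, before 24 weeks, are excluded from the denominator, in line with the 10.5 parenthesis, and word the Rule to match.
- State whether nivolumab-only cycles count towards the 6, and how a patient is classed who reaches 24 weeks with fewer than 6 cycles because of delays.
- Rerun the operating-characteristics table for the looks actually used and the boundaries actually printed.

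The cost is a few sentences and a new simulation, with no extra patients or data. Feasibility looks may then fall on different dates from futility looks.

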| 9 out of 16 patients.    | 0.685                                |
| 10 out of 17 patients.   | 0.760                                |
| 10 out of 18 patients.   | 0.676                                |
| 11 out of 19 patients.   | 0.748                                |
| 11 out of 20 patients.   | 0.668                                |

The table below shows the operating characteristics of this monitoring rule for the study. The results are based on 5000 simulated studies for each scenario.

| Assumed true risk
not feasible | Percent of times the study
stops for lack of feasibility | Average sample size |
|-----------------------------------|---|---------------------|
| 0.05                              | 0.1%  | 20.0                |
| 0.10                              | 0.8%  | 19.9                |
| 0.15                              | 2.6%  | 19.6                |
| 0.20                              | 6.3%  | 19.1                |
| 0.25                              | 12.2%   | 18.2                |
| 0.30                              | 18.0%   | 17.4                |
| 0.35                              | 28.8%   | 16.0                |
| 0.40                              | 40.7%   | 14.6                |
| 0.45                              | 54.1%   | 12.9                |
| 0.50                              | 67.5%   | 11.2                |
| 0.55                              | 79.5%   | 9.6                 |
| 0.60                              | 88.3%   | 8.3                 |
| 0.65                              | 94.3%   | 7.1                 |
| 0.70                              | 98.2%   | 6.2                 |
| 0.75                              | 99.6%   | 5.7                 |

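### Section 10.5: the feasibility boundary table labels its probabilities with the opposite event, and the threshold is given as both 67% and two thirds

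*Combined protocol and SAP*

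**What the plan says.** All of this is in section 10.5, Feasibility monitoring, of the combined protocol and SAP.

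- **Decision quantity.** "We will base the decision on the posterior probability that the treatment is not feasible".
- **Prior.** "The prior distribution for this calculation is Uniform (0,1").
- **Threshold.** The opening statement begins "If there is considerable probability" and puts the figure at 67% or more. The end of the same paragraph restates it: "where we quantify certainty as two thirds or greater", glossed as 2:1 odds. The sentence labelled as the rule also uses two thirds, again with 2:1 odds.
- **Boundary table.** The left column lists how many patients out of n must be unable to complete treatment for the rule to stop, from 4 of 5 to "11 out of 20 patients". The right column is headed "Probability that feasibility > 50"% and runs from 0.891 to 0.668.
- **Timing.** The text places the feasibility analysis at each interim analysis. Section 10.4 puts those at 10 and 15 patients, with the final analysis at 20. The table itself starts at the fifth patient.

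**The concern.** The two columns of the table do not fit together. If 4 of 5 patients cannot complete treatment, a probability of 0.891 that more than half of patients can complete it is implausible under a flat prior. The section's own decision quantity is the probability of the opposite event. A monitor or committee member who quoted the column as labelled would report an 89% chance that the regimen is feasible, when the plan's calculation gives 11%.

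The two thresholds look like one number and its rounding. They would matter only if a boundary row fell between 0.6667 and 0.67. The last printed value, 0.668, does.

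**Working it through.** **Inputs, all from section 10.5.** Prior Beta(1,1); x infeasible of n; cut-off 50%; thresholds 2/3 and 0.67; the 16 printed boundaries.

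**Formula.** The posterior for the infeasibility rate is Beta(1+x, 1+n−x). At a cut-off of one half, its upper tail equals the chance that a Binomial(n+1, 1/2) count is at most x.

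**Reproducing the printed values.**

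- 4 of 5: (1+6+15+20+15)/64 = 57/64 = 0.8906; printed 0.891.
- 11 of 20: 1,401,292/2,097,152 = 0.6682; printed 0.668.

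| Boundary | Printed | P(infeasibility > 50%) | P(feasibility > 50%) |
|---|---|---|---|
| 4 of 5 | 0.891 | 0.8906 | 0.1094 |
| 6 of 10 | 0.726 | 0.7256 | 0.2744 |
| 9 of 15 | 0.773 | 0.7728 | 0.2272 |
| 11 of 20 | 0.668 | 0.6682 | 0.3318 |

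The other 12 rows also agree to three decimals with the third column. None agrees with the fourth, which is what the header names.

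**Comparing the thresholds.** For each n from 5 to 20, find the smallest x whose posterior reaches the threshold.

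- At 2/3, all 16 printed boundaries are recovered.
- At 0.67, 15 are unchanged. At n = 20, 0.6682 falls short and the boundary becomes 12 (posterior 0.8083).

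**Effect of 12 instead of 11 at n = 20.** These are exact sequential binomial probabilities of crossing a boundary at any look, with the other boundaries as printed.

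| True infeasibility | Every patient 5–20: 11 vs 12 | Difference | Looks at 10, 15, 20: 11 vs 12 | Difference |
|---|---|---|---|---|
| 0.50 | 61.6% vs 59.7% | 1.9 points | 52.1% vs 45.6% | 6.5 points |
| 0.55 | 75.5% vs 73.4% | 2.1 points | 68.1% vs 60.9% | 7.2 points |
| 0.60 | 86.4% vs 84.5% | 1.9 points | 81.6% vs 75.1% | 6.5 points |

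These figures come from the printed boundaries and serve only to compare 11 with 12. They do not reproduce the simulated stopping percentages in section 10.5 (67.5% at a true risk of 0.50, for example), which is a separate matter.

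**The case against.** The best defence is that neither slip changes what a monitor would do. The rule sentence, the text before it and the row label all point to stopping when infeasibility is probable. A monitor acts on the counts, and all 16 are right at two thirds. The 67% figure appears once, in introductory prose about considering a stop, and reads naturally as 2/3 rounded to a whole percent. At 20 patients there is little accrual left to halt. The text also judges feasibility among patients who have not progressed or died before 24 weeks. If those alone form the denominator, an arm capped at 22 enrolled would seldom supply 20 such patients.

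Most of that stands, and it rules out four stronger readings.

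- A reader might infer from the header that the rule stops an arm when the regimen looks feasible. Every operative statement says the opposite.
- A reader might call the outcome at 11 of 20 undefined. The rule and the table both say stop; only the rounded figure disagrees.
- A reader might size the disagreement by the simple chance of exactly 11 of 20, about 0.16 to 0.18 at true rates of 0.50 to 0.60. That ignores arms already stopped at earlier looks.
- Feasibility is listed as a secondary endpoint in section 10.1.2, so a reader might take the 20-patient row as the trial's final feasibility verdict. Section 10.1.2 attaches no success criterion, and section 10.2 makes the final analysis descriptive.

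The defence does not make the header correct, and it does not reconcile the two thresholds.

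**Conclusion.** Wrong as written, of minor severity. The header misnames all 16 probabilities in a table that supports a stopping decision in each of three arms: 0.668 to 0.891 are printed where the named event has probability 0.109 to 0.332. No stopping count is affected.

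The threshold is inconsistent at one row, 11 of 20. The choice between 11 and 12 there moves the overall crossing probability by about 2 points with monitoring after every patient from the fifth, or 6 to 7 points with looks at 10, 15 and 20 only.

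Those sizes assume true infeasibility of 0.50 to 0.60, independent patients with a common rate, 20 patients counted for feasibility in the arm, and a feasibility look at 20. The finding about the header needs only the stated prior and the printed counts.

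**What to change.** In section 10.5:

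1. Relabel the right-hand column as the probability that infeasibility exceeds 50%.
2. Replace the 67% in the opening statement with 2/3, so that the section has one threshold.

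The cost is two wording changes. All 16 printed boundaries and values stay as they are, and no new data, simulation or analysis is needed for this point.

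### The feasibility operating-characteristics table in Section 10.5 does not follow from the printed stopping boundaries (it fits stopping at 3 of 5, not 4 of 5) or from the stated interim looks, so its stopping rates are too high

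*Combined protocol and SAP*

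**What the plan says.** Section 10.5 puts a Uniform(0,1) prior on the not-feasible rate and gives the criterion "Rule: Stop if there is two-thirds (2:1 odds) or greater probability that 50% or more patients cannot complete" the full six cycles, leaving aside patients who progressed or died. Boundaries are listed for every n from 5 to 20, beginning with "4 out of 5 patients" (0.891) and ending with 11 of 20 (0.668).

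On timing, the section says two things: "the analysis will occur at the time of each interim analysis", and later "The following table shows the stopping boundaries for monitoring that starts at the fifth patient". Section 10.4 sets the interim analyses at 10 and 15 patients per arm and the final analysis at 20.

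The section then states "The table below shows the operating characteristics of this monitoring rule for the study" and gives, for 15 true risks from 0.05 to 0.75, the percentage of studies stopped and the average sample size, from 5000 simulated studies per scenario.

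**The concern.** A table of operating characteristics should be reproducible from the rule printed above it. Here the printed stopping rates look too high for a rule that needs 4 failures in the first 5 patients. The printed average sample sizes, down to 5.7, are impossible if the first check comes at 10 patients.

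This table is the only evidence in the plan on how often the rule would stop an arm whose regimen most patients cannot complete, and how often it would wrongly stop a tolerable one. If it describes another rule, those who approved the monitoring plan relied on properties the trial will not have. The timing conflict also affects conduct: a monitor cannot tell from the text whether to act at the fifth patient or wait for the tenth.

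Two smaller matters sit in the same place. The boundary column is headed "Probability that feasibility > 50"%, but its values are the probability of the opposite event. And the posterior is defined through the share "of patients who do not progress or die before 24 weeks do not make it to 24 weeks", while the tables run to 20 without saying whether n counts only such patients.

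**Working it through.** **Inputs.** From Section 10.5: Uniform(0,1) prior, threshold 2/3, the 16 printed boundaries, 5000 simulations per row. From Section 10.4: looks at 10 and 15, final at 20.

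**Step 1: the boundaries.** With x not-feasible patients out of n, the posterior is Beta(1+x, 1+n−x), so P(rate > 0.5) = P(Bin(n+1, 0.5) ≤ x).

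- 4 of 5: 57/64 = 0.891, as printed.
- 3 of 5: 42/64 = 0.656, below 2/3, so no stop.
- 11 of 20: 0.668, as printed.

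All 16 printed values reproduce to three decimals, and each boundary is the smallest count that reaches 2/3. The same calculation shows the heading is reversed: 0.891 is the probability that the *not-feasible* rate exceeds 50%.

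**Step 2: operating characteristics.** Let g(n, k) be the probability of having seen n patients with k failures without stopping, and p the true risk. Before the check at n, f(n, k) = (1−p)·g(n−1, k) + p·g(n−1, k−1). The probability of stopping at n is S(n), the sum of f(n, k) over k at or above the boundary; those terms are then removed to give g(n, k). Total stopping is ΣS(n), and average N = Σn·S(n) + 20·(1 − ΣS(n)). This is exact.

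Each cell gives percent stopped / average N:

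| Risk | Printed table | Printed boundaries, every patient from 5th | Same, but 3 of 5 at n=5 | Looks at 10, 15, 20 |
|---|---|---|---|---|
| 0.20 | 6.3 / 19.1 | 2.3 / 19.7 | 6.2 / 19.1 | 0.7 / 19.9 |
| 0.25 | 12.2 / 18.2 | 5.6 / 19.3 | 11.4 / 18.4 | 2.2 / 19.8 |
| 0.30 | 18.0 / 17.4 | 11.3 / 18.6 | 19.0 / 17.3 | 5.7 / 19.5 |
| 0.35 | 28.8 / 16.0 | 20.1 / 17.6 | 28.9 / 16.1 | 12.1 / 19.0 |
| 0.40 | 40.7 / 14.6 | 32.1 / 16.2 | 40.9 / 14.5 | 22.2 / 18.2 |
| 0.45 | 54.1 / 12.9 | 46.5 / 14.6 | 54.3 / 12.9 | 36.0 / 17.2 |
| 0.50 | 67.5 / 11.2 | 61.6 / 12.9 | 67.7 / 11.2 | 52.1 / 16.0 |
| 0.60 | 88.3 / 8.3 | 86.4 / 9.4 | 88.8 / 8.2 | 81.6 / 13.3 |
| 0.75 | 99.6 / 5.7 | 99.4 / 6.2 | 99.5 / 5.7 | 99.1 / 10.6 |

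With looks at 10 and 15 only, stopping is 5.1% at 0.30, 18.6% at 0.40, 43.0% at 0.50 and 70.9% at 0.60.

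**Step 3: could it be simulation error?** The standard error of a percentage from 5000 runs is at most √(50×50/5000) = 0.7 points. Against the printed boundaries, the gaps at risks 0.20 to 0.50 are 4.0 to 8.7 points, about 9 to 20 standard errors of the respective rows. With 3 of 5 at n=5 and nothing else changed, every one of the 15 rows agrees within 1 point and 1.8 standard errors, and every average N within about 0.15.

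**Step 4: why one boundary matters so much.** At risk 0.40, P(at least 3 of 5) = 31.7% and P(at least 4 of 5) = 8.7%. The first look alone adds 23 points of stopping, only part of which the later looks would have produced anyway.

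**Step 5: other explanations tried.** Looks every five patients (with 4 of 5 or 3 of 5), a start at n=3 or n=4, omitting the check at 20, and a threshold of 0.5 all fit worse, and none fits all rows. A cut-off near 0.65 instead of 0.667 would admit 3 of 5 and leave the other 15 boundaries unchanged. That is a plausible source, but the documents do not state it.

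**The case against.** The best defence is that the boundaries, which decide when an arm stops, are right. Only a descriptive table is wrong. Feasibility is a secondary endpoint, the response-based futility rules do not use this table, and parts of Section 10.5 speak of considering a stop, although its rule line says to stop.

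The error also cuts both ways. The correct figures show fewer false stops of a tolerable regimen (2.3% instead of 6.3% at risk 0.20). For clearly infeasible regimens the gap against the printed boundaries is small: 1.9 points at 0.60, then 0.6, 0.5 and 0.2 points at 0.65, 0.70 and 0.75.

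On the denominator, the feasibility definition, the posterior definition and the rule line all set aside progression and death, so a table running to 20 may simply cover the largest possible n. The column heading is unlikely to mislead, because the neighbouring column is labelled correctly.

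Most of this stands as qualification. The heading and denominator are matters of wording, and the overstatement is concentrated between about 0.15 and 0.60. None of it makes the table that of the printed rule, and none of it resolves the two look schedules, which do affect conduct.

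**Conclusion.** The concern holds. The operating-characteristics table is not that of the printed boundaries under either look schedule in the text. If every patient is checked from the fifth, stopping is overstated by 4.0 to 8.7 points at risks 0.20 to 0.50, and average sample size is understated by up to 1.7 patients. If the checks fall at 10, 15 and 20, stopping is overstated by up to 18.5 points (40.7% against 22.2% at risk 0.40). The printed averages of 5.7 to 9.6 at risks of 0.55 and above cannot then occur. That 3 of 5 was used at the first look is inferred from the fit; that the table and rule disagree is arithmetic.

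These figures assume independent patients with a common risk and 20 informative patients per arm, the maximum the printed table allows. Patients who progress or die before 24 weeks are set aside, so fewer will be informative. The documents give no such rate for Arms D to F. As an illustration, ending the Step 2 recursion for the printed boundaries (from the fifth patient) at a fixed number of informative patients gives stopping at risk 0.50 of 42% for 8, 48% for 10 and 57% for 16, against 61.6% for 20.

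**What to change.** - Choose one look schedule, every patient from the fifth or the interim-analysis looks, and state it once, including whether the rule applies at 20. Reconcile Sections 10.4 and 10.5 accordingly.
- Recompute the table for the printed boundaries under that schedule, preferably exactly, and replace both the stopping percentages and the average sample sizes. The boundaries need no change at the two-thirds threshold.
- Rename the boundary column as the probability that the not-feasible rate exceeds 50%.
- State that n in the boundary table counts only patients who have not progressed or died before 24 weeks, as the posterior definition implies, and show the operating characteristics for a range of informative numbers below 20.

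The cost is one short calculation and corrected tables, with no change to sample size. The stated chance of stopping an infeasible regimen becomes less favourable, and the stated chance of wrongly stopping a tolerable one becomes more favourable.
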